# **Scientific Research Objectives**

The primary aim of this project is to provide proof-of-concept for the clinical effectiveness of the "exercising into discomfort" approach in patients with SSP. In the first three objectives, the focus will be on its effect on shoulder pain and functionality (patient-reported outcomes, objective 1), on scapular dyskinesis (objective 2), subacromial space, and the tendon structures (objective 3) during and after 3 months of exercise therapy in patients with SSP. In the fourth objective, the relationship between patient reported outcomes and the US measurements during the treatment course will be explored. Two groups will be compared in a randomized controlled trial (RCT): an intervention group "exercising into discomfort" (G1) and a control group "exercising without discomfort" (G2). The time points of assessment will be prior to the treatment at baseline (T0), at 6 weeks during treatment (T1), end of treatment at 12 weeks (T2), and follow up at 26 weeks (T3).

OBJECTIVE 1	To investigate the effectiveness of exercising into discomfort during a strength training program in the treatment of SSP on self-reported shoulder pain and function
Methods	Double Blind Randomized Controlled Trial comparing 2 groups (G1 versus G2), with SPADI (Shoulder Pain and Disability Index, a valid and reliable patient-reported outcome measure of pain and disability  ) as primary outcome. A "high pain monitoring model" will be used to monitor pain during and 1 hour after every exercise in G1 (see "intervention" in methodology).
Hypothesis	In G1 SPADI will be reduced more than in G2.
Novelty/ Relevance	If successful, the results of this study will lead to a reconceptualization of exercises in SSP, allowing pain (defined as discomfort sensation) to be an essential component and not a barrier in the physiotherapy treatment.

OBJECTIVE 2 ft	To investigate whether improvements in shoulder pain, function and quality of life is positively related with reduced presence of scapular dyskinesis
Methods	Scapular dyskinesis will be registered by visual observation at rest and during movements (abduction and flexion) and its effects on pain will be tested by scapular assistance test and scapular retraction test
Hypothesis	Scapular dyskinesis will decrease more in G1, in relation to the increase in strength and coordination of the scapulothoracic and scapulohumeral muscles.
Novelty/ relevance	Although the scapular control will be integrated in the exercises in both groups from the first session, we expect a greater improvement in G1 thanks to both increased muscle strength and regained self-efficacy in movement performance. Therefore, it is relevant to register how scapular dyskinesis is evolving during treatment in order to understand when and in which subgroups of patients it is contributing to symptoms of SSP.

OBJECTIVE 3	To investigate the effects of exercising into discomfort on changes in subacromial space (quantified as acromiohumeral distance AHD) and tendon structures measured by US imaging in SSP patients							
MethodsAnalysis of the secondary outcomes (subacromial space and tendon structure changes measured by US imaging) of the RCT conducted in objective 1								
Hypothesis	In both groups there will be an increase in the subacromial space and decrease in STT. These changes will be more evident in G1							
Novelty/ Relevance	The lack of understanding of tendon structural changes in "exercising into discomfort" in patients with SSP contributes to the inadequate management of this pathology. Information on such parameters will provide insights into the mechanisms behind this modality of exercise therapy during and after the end of the treatment. Moreover, this study aims to clarify the role of the subacromial space as a valuable indicator of SSP recovery. To the best of our knowledge, this is the first time that tendon structures are monitored during the treatment other than before and after rehabilitation (assessment at T2).							

OBJECTIVE 4 උ	To examine whether improvement in shoulder pain, function and quality of life is associated with changes in the subacromial space and tendon structures as measured by US imaging
Methods	Analysis of possible association between parameters measured by US (subacromial space, RC tendon thickness) and clinical symptoms (self-reported shoulder pain, questionnaires on functionality and quality of life) at T0, T1, T2, T3 in the RCT
Hypothesis	There will be a significant correlation between US imaging parameters and clinical symptoms
Novelty/ Relevance	There is contrasting evidence in the literature regarding the association between subacromial space and clinical symptoms. This study will elucidate this question and further enhance the knowledge regarding other significant tendon changes (i.e. combining AHD and RC thickness in the occupational ratio) during and after exercising into discomfort, laying the groundwork for future prognostic studies.

This project proposal is organized as a collaboration with other partner universities, relying on different expertise: [name] (University of Antwerp, Belgium) will be the main promotor of the PhD student currently and he is the world leading expert on shoulder pain (http://expertscape.com/ex/shoulder+pain); [name] (University of Malaga, Spain) will give guidance in the US training together with [name], who obtained a joint PhD degree (Malaga - Antwerp) on the use of US in rehabilitation for shoulder pain; [name] (University of Southern Denmark), expert on exercise therapy in shoulder pain and [name] (University College Rotterdam) expert on assessment and management of chronic musculoskeletal pain. They wrote the initial project for the grant at the University of Antwerp together and they gave and will give continuous assistance during all the phases of the project (definition of the intervention, feasibility study, reliability study on US measures, RCT).

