# Outcome measures

All outcomes will be measured at baseline (T0) and 6 (T1), 12 (T2), 26 (T3) weeks and the assessors will be blinded to group allocation. The **primary outcome** is the **difference in mean change between groups from T0 to T1, T2 (12 weeks, end of the treatment), and T3 (26 weeks, follow-up)** in the patient self-reported outcome score **Shoulder Pain and Disability Index (SPADI)**. This questionnaire is a patient-reported outcome measure (PROM) with high test–retest reliability and construct validity  and is available and validated in Dutch .

Secondary outcomes are registered for each patient at the same time points as the primary outcome, except for the Global Perceived Effect Score, which will be assessed after 1st treatment and then at 6 and 12 weeks. The secondary outcomes are:

**Scapular dyskinesis:** The procedure we will use is based on the procedures described by Tate et al.  and Struyf et al. . Scapular position will be observed at rest and during active loaded and unloaded humeral motion in a frontal and sagittal plane. The effect of scapular correction will be tested by means of the modified scapular assistance test and scapular retraction test . Reduction of pain during these tests compared with non-assistance during the same tests confirms scapular involvement in the shoulder complaints.

**Subacromial space**: Acromiohumeral distance (AHD) is a US measurement used to quantify the subacromial space. It is defined as the shortest linear distance between the most inferior aspect of the acromion and the humeral head . AHD is measured at 0 and 60 degrees of active shoulder elevation in the scapular plane, following the procedure of measurement indicated by Navarro-Ledesma et al . It has already been used to evaluate different populations, such as healthy volunteers  and patients with shoulder pain .

**Tendon changes**: Tendon structural changes (limited to RC thickness and long biceps) will be evaluated using US device and following international guidelines . STT will be also computed as percentage of subacromial space, known as the occupation ratio (using the formula [(STT/AHD)\*100] .

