# WP3: Data analysis

Statistical analyses will be performed using JMP ®Pro 14.0.0 (SAS Institute Inc., Cary, NC, USA) . Level of significance is set at p= 0.05. Appropriate descriptive statistics will be performed.

**OBJECTIVE 1,2,3:** A mixed regression model for repeated measures will be used to assess both the evolution of SPADI (pain and function), strength, ROM and US parameters within persons from baseline (T0) over time (T1, T2, T3) and the differences in evolution between subjects. Potential confounders are: age, gender, BMI, previous corticosteroid injections, severity of initial symptoms. They will be measured during the history taking at the first assessment and added into the mixed regression model as co-variants. If for a certain variable the percentage of missingness will be more than 15%, multiple imputation for missed observation will be used. There are three assumptions for the mixed regression model: change over time, a sensible measure for time (multiple time points of measure), normality of residuals (it will be checked using a Shapiro-Wilk test). If these residuals are not normally distributed, an appropriate transformation will be performed first. Therefore, this model best fits the longitudinal design of the RCT. **OBJECTIVE 4**: correlation analysis between tendon structures and clinical symptoms using the correlation for pairs of continuous variables in JMP.

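### Objective 4 tests an unspecified ultrasound–symptom correlation over many unadjusted pairs, so a chance significant result is likely and could be read as support

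*Combined protocol and SAP*

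**What the plan says.** The Objective 4 table in Scientific Research Objectives states the hypothesis: "There will be a significant correlation between US imaging parameters and clinical symptoms". The objective itself asks whether improvement in pain, function and quality of life "is associated with changes in the subacromial space and tendon structures as measured by US imaging", which points to change scores. The Methods row of the same table refers to "parameters measured by US (subacromial space, RC tendon thickness", and to the clinical measures "at T0, T1, T2, T3 in the RCT", which points to values at each visit.

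The analysis is one sentence in WP3: Data analysis: "correlation analysis between tendon structures and clinical symptoms using the correlation for pairs of continuous variables in JMP". The same section sets one general threshold: "Level of significance is set at p= 0.05". Neither place names a primary pair, visit, direction, size of correlation, number of tests or adjustment.

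On the status of the objective the documents pull two ways. The opening paragraph of Scientific Research Objectives says the relationship is to be explored. The end of the rationale and the novelty row of Objective 4 say the study will elucidate it, against a background of conflicting literature and as groundwork for prognostic studies.

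**The concern.** A prediction of a significant correlation, with no pair named, can be matched by any of dozens of correlations, each tested at 0.05. The more pairs are examined, the more likely that at least one falls below 0.05 when ultrasound findings and symptoms are unrelated. At n=44 such a pair must have |r| of about 0.30 or more, so a chance hit would look like a moderate association.

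At stake is what Objective 4 can contribute. The rationale says that studies already disagree on whether the acromiohumeral distance (AHD) tracks function, and that ultrasound could help tailor exercise. A pair selected after the fact from an unadjusted table would add to that disagreement and could be carried into later prognostic work.

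**Working it through.** **No figure to reproduce.** The documents give no count of correlations, error rate or power for Objective 4. The counts and the correlations among measures below are assumptions.

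**Inputs**
- Threshold per test: 0.05 (WP3: Data analysis), taken as two-sided because sidedness is not stated.
- Patients: 44, the target in the renewal's WP2: RCT.
- Time points: four visits if levels are correlated; three intervals if changes from T0 are.
- Ultrasound parameters: from Outcome measures, "AHD is measured at 0 and 60 degrees of active shoulder elevation in the scapular plane" (two parameters), plus cuff thickness, long biceps and the occupation ratio. The renewal's reliability table lists supraspinatus and subscapularis separately, giving six. It also lists coracohumeral distance at 0 and 60 degrees, giving eight. The Methods row of Objective 4 names only subacromial space and cuff thickness, so about three is also a fair reading.
- Clinical scores: SPADI, EQ-5D index and EQ VAS make three; a separate pain score makes four.

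**Number of tests** m = ultrasound parameters × clinical scores × time points
- Narrow: 3 × 3 × 3 = 27 (changes) or 3 × 3 × 4 = 36 (levels)
- Middle: 6 × 3 × 3 = 54 or 6 × 3 × 4 = 72
- Wide: 8 × 4 × 3 = 96 or 8 × 4 × 4 = 128

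**Expected false positives** = 0.05 × m. For 27 tests: 1.35. For 72: 3.6. For 128: 6.4.

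**Chance of at least one p<0.05 with no true association.** If tests were independent this is 1 − 0.95^m. They are not: measures overlap and visits repeat on the same patients, so the independent figure overstates the risk. The other two columns come from simulation (Pearson, two-sided, n=44, ultrasound and clinical data generated independently of each other).
- Moderate to strong: correlation 0.3–0.6 among ultrasound measures and 0.5–0.7 among clinical scores; across visits 0.6–0.9 and 0.5–0.7 respectively.
- Very strong: 0.8 among measures and 0.9 across visits, in both domains.

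| Tests | Independent | Moderate to strong | Very strong |
|---|---|---|---|
| 27 (changes) | 75% | 56–67% | 46% |
| 36 (levels) | 84% | 53–76% | 37% |
| 54 (changes) | 94% | 73–88% | 59% |
| 72 (levels) | 97.5% | 74–94% | 49% |
| 96 (changes) | 99% | 87–97% | 68% |
| 128 (levels) | 99.9% | 87–99% | 59% |

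**Size of a chance hit.** Critical |r| = t/√(42 + t²) with t = 2.018 on 42 degrees of freedom: 2.018/√46.07 = 0.297.

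**After the fix.** One pre-specified pair at 0.05 carries a 5% chance. A Bonferroni threshold over 72 tests would be 0.05/72 = 0.00069, and over 128 tests 0.05/128 = 0.00039. The simulated chance of any false positive then falls to about 2–5%.

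**The case against.** The strongest reply is that Objective 4 is exploratory. The objectives section says the relationship will be explored, the Methods row speaks only of possible association, and the hypothesis is a one-line expectation in a grant-style table. An unadjusted screen is acceptable for exploration. This stands in part: it makes the matter secondary and points to labelling as much of the remedy. It does not dispose of the point, because the same table attaches a significance hypothesis and the plan says the question will be elucidated.

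Second, the count is inferred. Coracohumeral distance appears only in the renewal and is never tied to Objective 4; biceps is not a cuff tendon; a fourth clinical score is a guess. This stands, and is why the range starts at 27. At that size the chance is still 56–67%, or 46% under very strong correlation.

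Three stronger readings are tempting and are not supported:
- A reader might infer that any one significant pair formally confirms Objective 4. No such decision rule is stated.
- A reader might infer that the hypothesis cannot fail. Under several assumptions above it would fail in a third to a half of null trials or more.
- A reader might infer that the four visits will be stacked as if independent. No passage says so, and stacking would be an alternative to testing by visit, not an additional problem.

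**Conclusion.** The point holds. As written, Objective 4 pairs an open-ended significance hypothesis with unadjusted pairwise testing. The chance of at least one spurious significant correlation is about 50–99% under moderate to strong assumed correlation, and about 37–68% under very strong correlation, against 5% for one named test. These figures rest on 27 to 128 tests, n=44, two-sided Pearson tests and correlations that the documents do not supply. The direction of the result does not depend on whether levels or changes are used: the lowest figure is still about seven times the nominal level.

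What follows is that a chance finding could be read as support, not that the plan declares it to be support. The objective is not primary, and the SPADI comparison between groups is untouched.

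**What to change.** In the Objective 4 table and in WP3: Data analysis:

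1. Name one ultrasound parameter, one clinical score, the scale (level or change) and one interval as the test of the hypothesis, and reword the hypothesis to refer to that pair. The choice is the sponsor's; change in AHD with change in SPADI from T0 to T2 is one example.
2. Report every other pair as r with a 95% interval, labelled exploratory. If p-values are shown, apply a Holm or false-discovery-rate correction.
3. If visits are combined, use a model with a patient random effect and visit as a factor.

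The change must be made before pooled ultrasound and symptom data are examined together. Unblinding in November 2022 is not the relevant cut-off, because a pooled correlation needs no allocation data and the renewal says objective measures are processed from June 2022.

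The cost is wording only, with no new patients or measurements. The downside is that fewer pairs can be called significant.

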### Research methodology and work plan

### WP1: Preparation of the trial

In the previous academic year 2018/2019 the PhD student focused on the preparation of the trial, which included different tasks reported in the work plan in Table 1 (page 10).

### Literature review and survey on current physiotherapy practice

The first task was to develop an intervention protocol for the modality "exercise into discomfort". In order to achieve this goal, a literature review on exercise therapy in SSP is being conducted. The PhD student collaborated also in a survey on current physiotherapy practice in Belgium and the Netherlands, which has been recently published in peer-reviewed journal (Task 1.1, work package WP1,Table 1). With this background information, the PhD student together with the research team designed the intervention (Task 1.2, WP1) during the academic year 2018/2019. After ethical approval, the successful recruitment of physiotherapists for the feasibility study started.

### Feasibility study

In the recruited private practice, the feasibility study is now ongoing (Task 1.3, WP1). It includes 12 patients, which will allow to test 80% of compliance rate, ranging between 0.78 and 0.84 within a 95% of confidence interval. This number was obtained with the "Score method incorporating continuity correction" reported by Newcombe et al. 

The feasibility study aims to: 1) test a high-pain monitoring model (which is the intervention applied in G1 -"exercise into discomfort"-) and the rate of adherence to this modality, 2) test the rate of recruitment at this private practice, 3) verify adverse effects 4) test the practicability of delivering clinical questionnaires via online survey Qualtrics, 5) provide an indication of the time needed to collect the data.

The high pain monitoring model is based on the pain monitoring model which has been previously used in many studies. The difference is that the pain during exercise is higher than in the previous studies until the 9th week, with certain caveats: 1) during the exercises, the patient should feel discomfort/pain exceeding the pain at rest, ranging between 4 and 7 on NPRS (Numeric Pain Rating Scale). During the last set of 10/15 repetitions pain should not exceed 7; 2) Discomfort/pain should return to baseline level after 1 hour; 3) Discomfort/pain should not increase from day to day. In the last phase of the treatment (between 9th and 12th week) the pain during exercise ranges between 0 and 2 on NPRS, in order to allow the patient to focus on more proprioceptive and sport/work related tasks. A preliminary analysis of the data on 6 patients at the 6-week follow-up showed that all the subjects attended at least 4/6 physiotherapy sessions and they were all adherent to the home exercise (at least 10/11 home exercises completed) except one patient. Two patients experienced a slight increase (1 point on NPRS) in the level of pain after the physiotherapy or home exercise in the first three weeks. Discussing with both physiotherapists and patients, this was related to an increased level of sport in the same period or due to additional treatment of the posterior capsule, which can provoke initially some pain. The physiotherapist adapted the exercise and from the 4th week onwards the pain decreased to initial levels after 1 hour of exercise. Moreover, it emerged that a measurement of the pain after 1day was necessary to evaluate the evolution of the pain after painful exercises. This will be added in the design of the RCT and it is also in line with the recent recommendation for evaluating pain during and after exercises.

The rate of recruitment at this private practice was 5 patients per month, which means we will be able to recruit 60 patients for the RCT at this practice in 1 year (WP2), thereby minimizing the recruitment risk inherent to RCTs. Two physiotherapists conducted an initial screening at the first visit based on the history taking, which allowed to exclude 37 patients. If considered eligible, the patients underwent to a second screening phase led by the PhD student: only 3 patients were excluded at this time point. The estimated time for the screening is 30 minutes while 1 hour is necessary for the rest of the measurements. Qualtrics proofed to be a practical modality of taking clinical questionnaires because no data were lost, and the patients who did not filled in the questionnaire within 2 days were sent a reminder.

#### Ultrasound measures

In May 2019 the US machine was bought with the budget of the doctoral grant. In August 2019 the PhD student followed a training on US imaging during a research stay of 4 days under the supervision of the US expert [name] at the partner University of Malaga (Task 1.4, WP1). In February 2020 this researcher came to Antwerp for a 2-week period to conduct an inter-reliability study on the US parameters previously decided and discussed during the research stay. This part of the project is currently in the phase of data analysis. This will allow to validate the skills of the PhD student as novice sonographer and to decide which US measures are valid and reliable to be part of the second phase (RCT, WP2). The US measures are described in WP2, under "Outcomes measures".

### Ethical approval and fine-tune protocol

Ethical approval for the original protocol has been already obtained from the Ethical Committee of the University of Antwerp. The reliability study and feasibility study have been added and approved by submitting two amendments. The whole protocol will be analysed and modified based on the feedback of the physiotherapists and the patients. A revision of the protocol after the feasibility study will be critically analysed together with the rest of the research team in April 2020 during one or more Skype meetings and, if necessary, also submitted as

amendment to the Ethical Committee.

# WP2: Randomized controlled trial

#### Design

This study will be conducted as an experimental randomized, controlled, doubleblind trial (RCT) in one physiotherapy practice in Belgium. The patients with SSP will be randomized into one of 2 groups (concealed, permuted block randomization of 2,4,6 size using randomisation.com), being either exercising into discomfort (G1) or exercising with slight/no discomfort (G2).

All training sessions will be applied for 12 weeks, three times weekly. The time points of assessment will be: before the start of the treatment (TO), at 6 weeks (T1), 12 weeks (T2), 26 weeks (T3). All participating patients will follow the flowchart illustrated in Figure 1.

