### Intervention

It corresponds to "Task 2.2", WP2 in Table 1 (page 10). Every physiotherapy session lasts 30 minutes and it includes 20 minutes of exercise therapy based on 4 strengthening exercises and 10 minutes of manual therapy (focusing on the release of posterior capsule). The manual therapy will be applied to all the patients without distinction to the two groups. The exercise therapy will be the distinct element between the two groups: group 1 (G1, exercising into discomfort) will execute exercises with pain intensity from 4/10 to maximum 7/10 on a NPRS scale, while group 2 (G2, exercising with slight/no discomfort) will execute not/slightly-painful exercises with pain intensity inferior to 2/10. These limits are set in order to ensure a clear difference in pain intensity between the two groups and a preliminary analysis of the feasibility study showed it was possible for the patient in G1 to train between 4 and 7/10 following the high-pain monitoring model. The pain level in G1 will decrease to 0-2 at 9th week so the patients can focus on more proprioceptive or sport/work related tasks. The exercises are individually prescribed and each patient will have 4 personalized strengthening exercises, with one focusing on the painful direction (which is usually abduction, flexion or external rotation) and the rest of exercises will elicit pain but not in the painful direction (for example, closed kinetic chain exercises or exercises with elastic bands). The aim in both groups is to gain strength in both scapulothoracic and scapulohumeral muscles, re-balancing the force couples in the shoulder joint during specific movements (i.e. re-train arm elevation in which a lower activity of serratus anterior and overactivation of the upper trapezius is present), without isolating one muscle during the exercise. Scapula stabilization exercises will be integrated with rotator cuff strengthening in one exercise (i.e. closed kinetic chain as push-up) from the first session, since recent studies showed that the order of exercise (scapular and then RC exercises or vice versa) was not affecting significantly the clinical outcomes. Our hypothesis is that a painful shoulder program focusing on strengthening exercises, with certain caveats, will load the shoulder muscles allowing a better and possibly faster recovery.

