#### WP3: Data analysis

Data analysis of the RCT (WP3, 3.4 and 3.5): demographics and other objective measures (strength, range of motion, scapular dyskinesis, data from the US machine) will be processed already from June 2022, but the data concerning the randomization process of two groups will be unblinded only at the end of the trial in November 2022. Related manuscripts: see **Manuscript 4 and 5**. The end of the data analysis will be **Milestone 3**. *Status:* Milestone 3 has been delayed from Q2 2022 (initial FWO project) to Q4 2023. This delay is due to a decrease in patient recruitment caused by the pandemic of Covid-19. However, thanks to the extension of the FWO scholarship, there will be sufficient time to recruit all patients and to conduct a thorough data analysis for both objective and subjective measures.

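### The trial is labelled double-blind without naming who is blinded; physiotherapists cannot be, patients cannot be blind to the exercise pain they feel, and the primary outcome is self-reported

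*Combined protocol and SAP*

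**What the plan says.** The label appears twice. The Design section under WP2 describes an "experimental randomized, controlled, doubleblind trial (RCT". The methods row of Objective 1, which also names SPADI as primary outcome, reads "Double Blind Randomized Controlled Trial comparing 2 groups (G1 versus G2". Neither place lists the blinded parties.

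Two levels of blinding are described elsewhere:
- Outcome measures: "the assessors will be blinded to group allocation".
- WP3: Data analysis, in the 2022 renewal's plan for the second term: the randomization data "will be unblinded only at the end of the trial in November 2022".

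Allocation is "concealed, permuted block randomization of 2,4,6 size using randomisation.com".

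The Intervention section defines the arms by pain during exercise. G1 "will execute exercises with pain intensity from 4/10 to maximum 7/10 on a NPRS scale"; G2 "will execute not/slightly-painful exercises with pain intensity inferior to 2/10". The limits are there to "ensure a clear difference in pain intensity between the two groups". The same part of the plan has the physiotherapist prescribe and progress the exercises according to the load that provokes pain. Under Adherence, patients keep an exercise and pain diary. Outcome measures describes SPADI as patient-reported.

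The renewal's account of the feasibility study (WP1) changes G1 from four painful exercises to one, with the other three at no or minimal pain. If that exercise stops provoking pain before nine weeks, a Borg exertion rating replaces the pain scale.

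**The concern.** Double-blind is usually taken to mean that at least the patient and one other party do not know the allocation. Here the treatment contrast is a sensation that the patient must notice and that the therapist must steer. The one trial role named as blinded, the assessor, does not produce the SPADI score; the patient does.

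What is at stake is how a SPADI difference is read. If therapists encourage the arms differently, or patients expect different results from painful and pain-free exercise, that can enter SPADI directly. A reader who relies on the label would treat a modest difference as free of such effects. A larger sample would not remove the bias.

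**Working it through.** **Role by role**

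| Role | What the documents support |
|---|---|
| Outcome assessors | Blinded (Outcome measures). Relevant to strength, ROM, scapular and ultrasound measures |
| Those handling data | Randomization data stay blinded until November 2022 (renewal, WP3) |
| Physiotherapists | No blinding described, and not possible: they set and adapt load to the arm's pain range (Intervention). Those from the feasibility study, which tested the G1 model, continue into the trial (Physiotherapist and patient recruitment) |
| Patients, to treatment received | No blinding described, and not possible: they exercise to a pain level and log pain |
| Patients, to the hypothesis or the other arm | Not stated in the documents reviewed |

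No procedure for blinding patients or physiotherapists is given, and no check of its success is planned.

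**What the plan's own figures allow**

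No SD or residual variance is given, and Sample size says the residual variance cannot be estimated from previous studies. So neither 54 patients (8 points, 90% power) nor 44 patients (10 points, 85% power) can be reproduced. Only a standard error (SE) can be back-solved from the revised statement in the renewal (WP2: RCT).

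*Inputs from the documents:* 10 points, 85% power, 5% level, 44 patients, 15% dropout (the dropout figure is from the initial calculation).
*Assumed:* two-sided test, equal arms, one SPADI comparison with a normal approximation, no true effect, and a differential reporting shift b of 2, 3 or 5 points.

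1. SE implied by the power statement: 10 / (1.960 + 1.036) = 10 / 2.996 = 3.34 points.
2. Patients per arm after dropout: 44 × 0.85 / 2 = 18.7.
3. SD that matches this SE: 3.34 / √(2/18.7) = 3.34 / 0.327 ≈ 10.2 points.
4. A less favourable assumed SD of 20: SE = 20 × 0.327 = 6.54 points.
5. False-positive rate = 1 − Φ(1.96 − b/SE) + Φ(−1.96 − b/SE).

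| Shift b (points) | SE 3.34 | SE 6.54 (SD 20) |
|---|---|---|
| 0 | 5% | 5% |
| 2 | 9.2% | about 6% |
| 3 | 14.6% | about 7% |
| 5 | 32.2% | about 12% |

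Example: for b = 3 and SE = 3.34, b/SE = 0.898, so 1 − Φ(1.062) + Φ(−2.858) = 0.144 + 0.002 = 14.6%.

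The rate depends on the absolute size of b, not its sign, so the table holds whichever arm the shift favours.

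**The case against.** The strongest reply is that the label may mean blinded assessors plus patients who do not know the hypothesis or what the other arm does. Both arms receive individualized strengthening, the same manual therapy and pain education, and feeling pain is not the same as knowing what is being tested. Consent pages were removed from the reviewed text, and the flowchart is not shown. This stands in part: patient unawareness of the hypothesis cannot be excluded, and it would be wrong to state that patients are unblinded in every sense. It does not rescue the label, because the plan nowhere gives this meaning and the physiotherapists know the arm in any case.

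Second, the contrast is narrower than the Intervention section suggests. Only one exercise of four is now painful, with the exertion fallback, and the Intervention section lowers G1 pain to 0–2 at the ninth week. The arms may be less obvious to patients as a result. Physiotherapists still deliver a known arm.

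Third, a reader might infer that the trial has no protection against bias, or that assessor blinding is the only safeguard. The documents do not support that. Concealed allocation guards against selection bias, late unblinding against bias in data handling, and assessor blinding against examiner bias in the measured outcomes. The plan also never claims in words that blinding protects SPADI; it only applies the label.

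Fourth, the illustration rests on assumed shifts of unknown direction and on a back-solved SE, and it reduces a mixed model over three follow-up times to one comparison. That is correct, and it is why a range is shown.

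**Conclusion.** The label is not supported for physiotherapists, nor for patients' awareness of the treatment they receive, and the blinding that is described does not cover self-report on SPADI. This follows from the documents' own description of the arms and the outcome, and does not depend on the arithmetic.

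The size of any bias is unknown. Under the stated assumptions, a shift of 2 to 5 points raises a nominal 5% false-positive rate to between about 9% and 32% at the back-solved SE, or between about 6% and 12% at an SD of 20. A reader might take 32% as the expected error rate; it needs both the small SE and a shift of half the 10-point target.

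A reader might also conclude that a SPADI benefit should count only if strength and ROM improve too. The documents do not support that rule. Isometric strength and active ROM depend on patient effort, and the plan's rationale includes pain modulation, fear avoidance and self-efficacy, so a SPADI gain without a strength gain could be the hypothesised effect.

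**What to change.** In Objective 1 and in the Design section, replace double-blind with a role-by-role statement:
- outcome assessors blinded for strength, ROM, scapular and ultrasound measures;
- randomization data kept blinded until the end of the trial;
- physiotherapists not blinded;
- patients not blinded to the exercise pain they experience, with a statement of whether they are kept unaware of the hypothesis;
- SPADI self-reported.

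Add a sentence that the SPADI result will be reported as open to reporting bias.

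This changes wording only: treatment, data collection, analysis and sample size stay as they are. It therefore remains feasible with 42 of the 44 patients already recruited by the end of April 2022. The price is a less favourable design label in the publications.
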